1.2. Study Flow Chart

Evaluation	Visit 1	Visit 2	Visit 3 Final Visit follow-up Day 22 ± 2/ETV
	Day 1 Baseline	Day 15 ± 2	
Informed Consent	X		
Inclusion/Exclusion Criteria	X		
Pregnancy test for females	X	X	
Eligibility/Enrolment	X		
Demography	X		
Medical/Surgical history (ocular &systemic)	X		
Review of current medical conditions (ocular & systemic)		X	X
Prior and concomitant medications (ocular & systemic)	X	X	X
External Ocular Examination	X	X	X
VAS ocular tolerability assessment	X**	X**	X
SANDE questionnaire	X	X	X
Best corrected distance visual acuity	X	X	X
Slit lamp examination (SLE)	X	X	X
Central corneal sensitivity by Cochet-Bonnet aesthesiometry	X	X	X
Tear collection for Lubricin dosing	X***	X***	X****
Tear Film Break Up Time (TFBUT)	X	X	X
Corneal fluorescein staining (Oxford score)	X	X	X
Schirmer's test (ST) I without anesthesia	X	X	X
Intraocular pressure (IOP)	X	X	X
Self-administration at home	X*	X*	
First Administration at study site	X	X	
Compound Dispensing	X		
Adverse events	X	X	X

*Self-administration at home during the study period

** pre-dose, 15 minutes post-dose, 30 minutes post-dose

*** pre-dose – in both eyes, 15 minutes post-dose in the right eye, 30 minutes post-dose in the left eye

**** both eyes

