6.3.7. Total Number of Randomized Subjects

30 subjects (10 per arm) will be randomized to 1:1:1 ratio.

Recruitment will proceed until the planned number of randomized subjects is achieved.

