7.3 Expected Drop-out Rate

An anticipated 10% drop-out of the randomized subjects will be expected

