8.1 Tables, listings and figures layout

Tables, listings and figures will be provided according to the following settings:

- Background: White
- Foreground: Black
- Font face: Times
- Font style: Roman
- Font size: 10 pt
- Font weight: Medium (data, footers and notes), Bold (titles and headers)
- Font width: Normal
- Layout: Landscape
- Top Margin: 1.3 cm
- Bottom Margin: 1.3 cm
- Left Margin: 2 cm
- Right Margin: 2 cm
- Test labels: Lubricin 20 µg/mL, Lubricin 50 µg/mL
- Control label: Vismed® 0.18%
- Date format: ddMMMyyyy
- Means, standard deviations, percent coefficient of variations, medians, lower confidence limits and upper confidence limits will be rounded to one digit more than the original data
- Minima and maxima will keep the same number of decimal digits as the source values
- p-values will be rounded to the fourth decimal digit and will be flagged by an asterisk (*) in case of statistical significance (i.e. p-value < 0.05 or, in case of centre by treatment interaction, p-value < 0.10)
- p-values lower than 0.0001 will be reported as "<.0001 *".

The data and results of Lubricin 20 µg/mL and Lubricin 50 µg/mL will be presented before the data and results of Vismed® 0.18% in all listings and tables.

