8.5 Handling of missing data

Not available data will be evaluated as "missing values". All data obtained will be used in the analysis and no imputation will be carried out for missing data to come from data not recorded in the CRF, from withdrawal of subjects from the study or from exclusion of subjects evaluated during the blind review meeting.

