8.11 Efficacy analysis

8.11.1 Primary efficacy analysis

The primary efficacy analysis will be performed on the subjects included into the Full Analysis Set.

Subjects will be analysed according to the treatment they actually received.

8.11.1.1 Tolerability using a Visual Analogue Scale (VAS) for dryness, foreign body sensation, burning/stinging, itching, pain, stick feeling, blurred vision and photophobia

The VAS values of each ocular symptom (i.e. dryness, foreign body sensation, burning/stinging, itching, pain, sticky feeling, blurred vision and photophobia) and their changes from day 1 - pre-dose values and day 15±2 - pre-dose values for the study/primary eye and for the non-study/secondary eye will be listed ([Listing 16.2.6.1](#)) and summarised by treatment and time point using descriptive statistics (mean, SD, CV%, minimum, median and maximum) ([Table 14.2.1.1](#)).

The VAS values of each ocular symptom for the study/primary eye and for the non-study/secondary eye will be analysed using an analysis of variance for repeated measures model. The model will include fixed effect terms for time point, baseline covariate (i.e. the day 1 - pre-dose value) and treatment. Time point will be specified as a repeated measurement. An unstructured covariance structure of the R matrix will be used and covariance parameters will be estimated using the restricted maximum likelihood method ([Table 14.2.2.1](#)).

Only the VAS values collected at Visit 1, Visit 2 and Visit 3 will be included into the analysis of variance for repeated measure model.

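### The SAP fits an unstructured REML model to the VAS in about 27 to 30 subjects, names no small-sample method and does not list its response time points; the effect is small with two responses and material only with six

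*SAP*

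**What the plan says.** SAP 8.11.1.1 describes the VAS model in some detail. On the mean structure: "The model will include fixed effect terms for time point, baseline covariate (i.e. the day 1 - pre-dose value) and treatment". On the covariance: "An unstructured covariance structure of the R matrix will be used and covariance parameters will be estimated using the restricted maximum likelihood method". There is no treatment-by-time term. The model is fitted for eight symptoms, in the study eye and in the fellow eye.

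On the data that enter: "Only the VAS values collected at Visit 1, Visit 2 and Visit 3 will be included". The flow chart in Protocol 1.2 schedules the VAS at three moments within each of Visits 1 and 2 ("pre-dose, 15 minutes post-dose, 30 minutes post-dose") and once at Visit 3.

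On size: "30 subjects (10 per arm) will be randomized to 1:1:1 ratio" (Protocol 6.3.7), and "An anticipated 10% drop-out of the randomized subjects will be expected" (Protocol 7.3). On incomplete data: "no imputation will be carried out for missing data" (SAP 8.5). SAP 8.11.2 plans no sensitivity analysis.

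On reporting, SAP 8.1 says that p-values below 0.05 "will be flagged by an asterisk (*) in case of statistical significance". SAP 8.3 calls the study exploratory and disclaims formal tests of Lubricin against the control. Neither document names Kenward-Roger, Satterthwaite or any other denominator-df or small-sample method.

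**The concern.** Unadjusted model-based standard errors treat the estimated covariance matrix as if it were known. In this model that matters in a particular way. With no treatment-by-time term, the treatment effect is a weighted average over the response time points, and the weights come from the estimated covariance matrix. Choosing weights from the same small sample does two things: it makes the estimate more variable, and it makes the reported variance too low. Both effects grow with the number of responses, because an unstructured matrix for k responses has k(k+1)/2 parameters: 3 for two responses and 21 for six.

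At stake are the asterisks in the VAS model table and the width of any interval drawn from this model. The SAP justifies its sample size by confidence-interval precision (8.4), so intervals that are too narrow would work against the study's own rationale.

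**Working it through.** **The plan's own figures.** SAP 8.4 reproduces. Means: 2 × 10² × 1.96² / 9² = 9.49, rounded up to 10. Proportions: 1.96² × (0.15 × 0.85 + 0.45 × 0.55) / 0.4² = 9.004, rounded up to 10. The documents state no error rate for the VAS model, so there is none to reproduce.

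**Inputs.** n = 30, or 27 after 10% drop-out. The model spends four between-subject parameters (intercept, baseline, two treatment terms), so ν = 30 − 4 = 26. The number of responses k runs from 2 (Visit 2 pre-dose, Visit 3) to 6 (adding 15 and 30 minutes at Visits 1 and 2). Not in the documents, and therefore assumed: unadjusted standard errors, df = ν, and the correlation between readings.

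**Hand approximation, complete data.** Estimating the weights multiplies the true variance by about (ν−1)/(ν−k), and the reported variance is about (ν−k+1)/ν of the value with known weights. Hence

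model SE / true SE ≈ √[ (ν−k+1)(ν−k) / (ν(ν−1)) ]

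and the actual size is about P( |t with ν−k+1 df| > 2.056 × that ratio ), where 2.056 is the 5% two-sided t value on 26 df.

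- k = 2: √(25 × 24 / 650) = 0.961; 2.056 × 0.961 = 1.975; on 25 df, 5.9%.
- k = 3: √(24 × 23 / 650) = 0.922; threshold 1.894; on 24 df, 7.0%.
- k = 6: √(21 × 20 / 650) = 0.804; threshold 1.652; on 21 df, 11.3%.

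With 27 complete subjects (ν = 23, t value 2.069) the results are 6.1% for k = 2 and 12.5% for k = 6.

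**Simulation.** Null trials were simulated under the SAP model (time, baseline, treatment, unstructured R, REML), with 800 to 5,000 replicates per setting. Correlation was constant at 0.3 to 0.8, or autoregressive with changing SD. Tests used unadjusted standard errors and between-subject df.

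| Responses | Covariance parameters | Arm v control, nominal 5% | 2-df treatment test | Model SE below empirical SE |
|---|---|---|---|---|
| 2 | 3 | 5.3–6.3% | 6.0–6.8% | 1–5% (e.g. 2.97 v 3.10) |
| 3 | 6 | 6.5–7.4% | 7.8–8.2% | 7–9% |
| 6, complete data | 21 | 9.1–12.0% | 12.3–14.9% | 17–20% (e.g. 2.27 v 2.84) |
| 6, 3 of 30 drop out | 21 | 13.3% | 15.8% | 23% (2.27 v 2.93) |

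The three-response row only shows the trend; no evident reading of the SAP gives three. A normal (Wald z) reference instead of 26 df gives 6.2–7.6% with two responses and 12.0–14.9% with six.

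**Where the excess comes from.** Adding a treatment-by-time term and testing one visit with two responses gives 5.3%, with model SE 3.62 against empirical 3.67. No weights are then estimated and the excess almost disappears.

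**With Kenward-Roger.** The contrast test runs at 4.5–5.4% (two responses), 5.1% (three), 5.7–6.7% (six, complete data) and 8.4% (six, 10% drop-out).

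**Asterisks.** Eight symptoms in two eyes make up to 16 fits. With one 2-df treatment p-value per fit, the expected number of false asterisks under the null is 16 × 5% = 0.8 at nominal size. It is 16 × 6% to 16 × 7% = 0.96 to 1.12 with two responses, and 16 × 12% to 16 × 16% = 1.92 to 2.56 with six.

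**The case against.** The strongest reply is that the six-response model is probably not what the SAP intends. Every scheduled VAS reading falls at Visit 1, 2 or 3, so a sentence restricting the model to those visits would exclude nothing if the post-dose readings were in. SAP section 8 lists three evaluation time points, one per visit. Protocol 7.1.4 introduces this analysis for the VAS taken before any ophthalmic assessment at a visit. With the Day 1 pre-dose value as covariate, two responses remain. The excess is then slight: in 3,000 replicates the Monte Carlo standard error at 5% is √(0.05 × 0.95 / 3000) = 0.4 percentage points, so a contrast rate of 5.5% is hard to tell from nominal.

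Much of this stands. A reader might infer that the primary VAS analysis runs at 12%; the documents do not support that as a general statement. But they do not exclude it either. If the Day 1 pre-dose value is only a covariate, the remaining Visit 1 values that could be responses are the 15- and 30-minute readings, and the sentence names Visit 1 among the values included.

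It is also fair to say that the SAP is silent on a correction and does not rule one out. A reader might infer that uncorrected standard errors are planned; the text does not say so. It leaves the choice to whoever programs the analysis.

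Finally, SAP 8.3 disclaims formal tests and regulatory claims, and 8.11.1.1 specifies no contrast or interval from this model. So no confirmatory error rate is at risk. The asterisk rule in 8.1 still applies, and it is read at 0.05.

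**Conclusion.** The point holds as a minor, inexpensive improvement. Two things are left open in SAP 8.11.1.1: how standard errors and df are computed, and which readings are responses. Under unadjusted standard errors with between-subject df, a nominal 5% contrast runs at about 5.5–6% with two responses (2-df test about 6–7%), which would rarely change an interpretation. It runs at about 9–12% (2-df test about 12–16%) only if the post-dose readings make six responses, and with 10% drop-out as well the contrast reached 13.3%.

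These figures rest on assumed df, assumed correlations and normal data; the documents supply only the sample size, the model terms and the drop-out rate. The consequence is confined to the asterisks and to any intervals taken from this model in an exploratory study.

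**What to change.** Make two additions to SAP 8.11.1.1 before database lock:

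1. State that standard errors and denominator degrees of freedom use the Kenward-Roger method.
2. List the response time points explicitly, with the Day 1 pre-dose value as covariate only; for example, Visit 2 pre-dose and Visit 3 as the responses.

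The second is needed as well as the first, because Kenward-Roger still leaves 8.4% with six responses and 10% drop-out. It also closes a separate trap: if the Day 1 pre-dose value were kept as a response while also serving as covariate, the fit degenerates, with the treatment estimate and its standard error both going to about zero.

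The cost is one model option, one sentence and slightly wider intervals. With two responses the typical standard error moves from 2.97 to 3.08, about 4% (3.08 / 2.97 = 1.04). With six it would move from 2.27 to 2.67, about 18% (2.67 / 2.27 = 1.18), which is mostly the width that was missing. No data collection changes.

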8.11.2 Sensitivity analyses

No sensitivity analysis is planned.

8.11.3 Subgroups analyses

No subgroup analysis is planned.

8.11.4 Secondary efficacy analysis

The secondary efficacy analysis will be performed on the subjects included into the Full Analysis Set.

Subjects will be analysed according to the treatment they actually received.

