7.1.2 Definitions

A subject will be defined as screened after the signature of the informed consent, regardless of the completion of all the screening procedures.

A subject will be defined as randomized in the study if he/she is assigned to a treatment arm (Test 1 (20 µg/mL), Test 2 (50 µg/mL) or Control).

- Enrolled set: all enrolled subjects. This analysis set will be used for demographic, baseline and background characteristics
- Full Analysis Set (FAS): all randomized subjects, who receive at least one dose of the ID. This analysis set will be used for the efficacy analysis
- Safety set: all subjects who receive at least one dose of the investigational medicinal product(s). This analysis set will be used for tolerability and safety analyses

Each subject will be coded by the CRO Biometry Unit as valid or not valid for the Enrolled set, FAS and Safety set. Subjects will be evaluated according to the treatment dose they will actually receive.

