1 INTRODUCTION

Statistical analysis will be performed by the CRO Biometry Unit. The endpoints and methods of analysis specified in this SAP are consistent with ICH E6 (R2), E9 and ISO14155-2012 guidelines (2, 3, 4). The SAP has been compiled by the CRO Biometry Unit on the basis of the final version 2.0 of the clinical investigational plan (5), reviewed by the Sponsor and finalized before the database lock and the treatment unblinding.

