8.2 Analysis sets

8.2.1 Definitions

A subject will be defined as screened after the signature of the informed consent, regardless of the completion of all the screening procedures.

A subject will be defined as randomized in the study if he/she is assigned to a treatment arm (Lubricin 20 µg/mL and Lubricin 50 µg/mL or Vismed® 0.18%).

- **Enrolled Set:** all enrolled subjects. This analysis set will be used for demographic, baseline and background characteristics
- **Full Analysis Set (FAS):** all randomized subjects, who receive at least one dose of the ID. This analysis set will be used for the efficacy analysis
- **Safety Set:** all subjects who receive at least one dose of the investigational medicinal product(s). This analysis set will be used for tolerability and safety analyses

Each subject will be coded by the CRO Biometry Unit as valid or not valid for the Enrolled set, FAS and Safety set. Subjects will be evaluated according to the treatment dose they actually received.

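### FAS efficacy is grouped by product received, not by randomised arm, so any dispensing mismatch would alter the randomised comparison (minor and conditional)

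*SAP*

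**What the plan says.** SAP 8.2.1 defines the FAS as "all randomized subjects, who receive at least one dose of the ID. This analysis set will be used for the efficacy analysis". Membership therefore depends on having been randomised and dosed.

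The arm in which a subject is counted is settled differently. SAP 8.2.1 gives a general rule after listing the three analysis sets: "Subjects will be evaluated according to the treatment dose they actually received". Protocol 7.1.2 has its counterpart: "Subjects will be evaluated according to the treatment dose they will actually receive".

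The efficacy sections repeat the rule:

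- SAP 8.11.1: "The primary efficacy analysis will be performed on the subjects included into the Full Analysis Set", followed by the as-treated sentence.
- SAP 8.11.4: "The secondary efficacy analysis will be performed on the subjects included into the Full Analysis Set", followed by "Subjects will be analysed according to the treatment they actually received".

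The same sentence appears in SAP 8.7 for the Enrolled Set and in SAP 8.12 for the Safety Set. Neither document provides an efficacy analysis by randomised arm, and SAP 8.11.2 plans no sensitivity analysis.

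**The concern.** The FAS is built from randomised subjects, but its arms are formed by something that happens after randomisation, namely which product was used. Protocol 6.4.3 relies on randomisation and masking to limit bias. Randomisation protects a comparison only while subjects stay in the arm to which they were allocated.

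The comparisons at stake are real ones. SAP 8.11.4.1 to 8.11.4.8 plan between-treatment Student's t tests, with a Wilcoxon test for the slit lamp grades. SAP 8.11.1.1 fits a repeated-measures model with a treatment term to each VAS symptom. SAP 8.1 flags p-values below 0.05. With 10 subjects per arm (protocol 6.3.7), one subject is 10% of an arm, and no planned analysis would show whether regrouping had mattered.

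**Working it through.** **Inputs.** From SAP 8.4.1: VAS mean change -20 mm in all three arms, SD 10 mm, target half-width of the 95% confidence interval 9 mm. From SAP 8.4.2: TEAE proportions 0.15 (each Lubricin arm) and 0.45 (control), target half-width 0.40. From protocol 6.3.7: 10 per arm. The documents give no misallocation rate, so a range of 0 to 2 wrong-product subjects in one arm is an assumption.

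**Step 1: the plan's own figures.** With z = 1.96:

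- VAS: 2 × 10² × 1.96² / 9² = 9.485, rounded up to 10.
- TEAE: 1.96² × (0.15 × 0.85 + 0.45 × 0.55) / 0.40² = 9.003, rounded up to 10.

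Both agree with the SAP. The grouping rule does not affect them.

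**Step 2: precision.** The VAS half-width at 10 v 10 is 1.96 × 10 × √(1/10 + 1/10) = 8.77 mm. With one subject moved (9 v 11) it is 1.96 × 10 × √(1/9 + 1/11) = 8.81 mm. Precision hardly changes, so the only issue is where the estimate lands.

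**Step 3: one subject moved.** Put every subject at the common mean except one, who lies d mm above it. That subject is assigned to arm A but receives the product of arm B.

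- By randomised arm, A - B = +d/10.
- By product received, A keeps 9 subjects at the mean and B has 11, so A - B = -d/11.
- Shift = d × (1/10 + 1/11).

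For d = 20 mm (2 SD): +2.0 mm becomes -1.8 mm, a shift of 3.8 mm. For d = 10 mm (1 SD): +1.0 mm becomes -0.9 mm, a shift of 1.9 mm. This treats VAS as a simple difference in means, not as the planned repeated-measures model. The secondary endpoints have no planning SD. On their own scales the same formula gives 0.38 SD and 0.19 SD.

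**Step 4: expected bias.** Simulation of 200,000 trials: two arms of 10, mean -20 mm and SD 10 mm in both, no true difference, two-sided t test at 0.05, with 0, 1 or 2 subjects of one arm counted in the other.

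- None switched: the two groupings are identical.
- Switch unrelated to outcome, 1 or 2 subjects: bias about 0 and type I error about 5.0% under either grouping.
- Switched subjects are those with the worst outcome (an extreme case): the as-treated bias is -3.1 mm with type I error 9.3% for one subject, and -5.3 mm with 19.9% for two. Grouped as randomised, bias stays about 0 and type I error about 5.0%.

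**The case against.** The strongest reply is that the rule may never operate. Dropout, missed doses and early stopping do not move a subject between arms; only receipt of another product does. Product is masked and one multidose container covers both weeks (protocol 2.3.1). Treatment is assigned by randomisation number on Day 1 (SAP 6.4). A masked error at first dispensing would come before every post-dose outcome, so there is no evident way for it to depend on outcome. The other supply route is replacement after loss (protocol 6.2.3). All of this stands, and it makes the extreme case in Step 4 a bound, not a forecast. If the products truly differ and the error is random, as-randomised grouping also has a price: one wrong-product subject in 10 dilutes the difference by a tenth.

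The trial is also exploratory, with no regulatory claim and no formal hypothesis test against control (SAP 8.3). The rule is prespecified and consistent between documents. Protocol deviations and kit identifiers are listed (SAP 8.7.5, 8.9) and the randomisation list is attached to the report (SAP 6.3), so an as-randomised result could be rebuilt afterwards. This lowers the severity. It does not remove the point, because a grouping chosen after unblinding can be questioned as data-driven.

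VAS needs care. Protocol 7.1.2 assigns tolerability to the Safety Set and protocol 7.1.4 places VAS under tolerability and safety, where grouping by treatment received is appropriate. SAP 8.11.1 nevertheless runs it as efficacy on the FAS. The fix has to respect both.

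A reader might also infer that the SAP contradicts its own commitment to ICH E9. The documents do not support that. SAP 1 says only that "The endpoints and methods of analysis specified in this SAP are consistent with ICH E6 (R2), E9", together with ISO 14155, and SAP 8.2.2 cites E9 for reasons for exclusion from the FAS. Neither ties E9 to the choice of arm.

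**Conclusion.** The point holds as a minor one. The plan groups FAS efficacy by product received and offers no analysis by randomised arm, so any mismatch would change the groups compared.

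It would be too strong to say that the randomised comparison is already lost. The rule has no effect without a mismatch, and the documents record none and give no rate. Nor is 3.8 mm an expected bias. It is the shift from one deliberately chosen 2 SD subject, it falls to 1.9 mm at 1 SD, and both lie inside the planned 9 mm precision. With no true difference and a mismatch unrelated to outcome, the expected bias is about 0. Material bias (-3.1 mm for one subject, -5.3 mm for two) needs the worst-outcome subjects to be the ones switched, which the masked supply makes unlikely. These figures rest on the SAP's SD of 10 mm, 10 per arm and an assumed 0 to 2 switched subjects.

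**What to change.** - In SAP 8.2.1 and protocol 7.1.2, replace the single rule with two: FAS efficacy analyses are by randomised arm, and Safety Set analyses are by treatment received.
- In SAP 8.11.4, and in 8.11.1 for the VAS model that the SAP runs as efficacy on the FAS, replace the as-treated sentence with analysis by randomised arm. Leave SAP 8.12 as it is.
- Because the protocol assigns tolerability to the Safety Set, add that VAS will also be shown by treatment received if any mismatch occurs.
- State that any subject whose product received differs from the one assigned will be identified in the existing deviation and kit listings.

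The cost is wording in the SAP and protocol, settled before unblinding. Sample size, visits, data collection and statistical models do not change. If no mismatch occurs, neither do the results.
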